## 4.2 Exclusion criteria

- 4.2.1 WHO classification of chronic myelomonocytic leukemia (CMML), RAEB-1, RAEB-2, AML
- 4.2.2 Treatment with horse or rabbit ATG or Campath within 6 months of study entry
- 4.2.3 Subjects with liver cirrhosis including subjects infected with Hepatitis B or C
- 4.2.4 Subjects with HIV
- 4.2.5 Infection not adequately responding to appropriate therapy
- 4.2.6 History of malignancy treated with chemotherapy and cytogenetic abnormalities suggestive of secondary myelodysplasia.
- 4.2.7 Moribund status or concurrent hepatic, renal, neurologic, pulmonary, infectious, or metabolic disease of such severity that it would preclude the patient's ability to tolerate protocol therapy
- 4.2.8 Life expectancy of less than 3 months
- 4.2.9 Hypersensitivity to eltrombopag or its components
- 4.2.10 Female subjects who are nursing or pregnant or are unwilling to take oral contraceptives or refrain from pregnancy if of childbearing potential
- 4.2.11 Unable to understand the investigational nature of the study or give informed consent or does not have a legally authorized representative or surrogate that can provide informed consent per section 10.5

## 5. TREATMENT PLAN

### 5.1 Administration of study drug (eltrombopag)

Subjects will initiate study drug at 50 mg orally once a day, taken on an empty stomach one hour before or at least two hours after a meal as detailed in section 5.8. Subjects of East Asian ancestry such as Japanese, Chinese, Taiwanese and Korean subjects will initiate study drug at 25 mg orally once a day.

### 5.2 Dose Adjustments (increases/decreases) of Eltrombopag (See section 2.6)

Patients will be enrolled on study because of anemia and/or thrombocytopenia. The majority of patients are expected to have cytopenias in both cell lines lineages, however some patients will have normal or close to normal counts in one or the other lineage at baseline. Therefore, dose adjustment criteria will vary depending on whether one or both lineages meet inclusion criteria, however dose adjustment will occur via the tables below and continue to the maximum dose until the inclusion criterion lineage or lineages responds, according to the schema set out below, unless toxicity-related stopping or dose reduction lab values occur. Note that patients entering the study based on anemia, with normal or near normal platelet count, will be expected to have an increased

in their platelet count on eltrombopag, but dose escalation for anemia will not be halted unless the platelet count goes above 400,000/ $\mu$ L. For patients entering meeting both anemia and thrombocytopenia eligibility criteria, dose escalation will not stop until both lineages reach the thresholds given below to stay on the current dose, unless platelets go over 400,000/ $\mu$ L or hemoglobin goes over 16.0 gr/dL, in which case drug will be discontinued for one week and the dose decreased by 50%. If the stopping platelet count or hemoglobin is reached regardless of entry criteria eltrombopag will be discontinued for one week and restarted at the next lowest dose.

**Dose Adjustments for Patients Entering with Platelets  $\leq$  30,000/ $\mu$ L or transfusion-dependence:**

Depending on response and/or tolerability, the daily dose may be increased or decreased according to the following rules:

Platelet Count <math>\leq</math> 30,000/<math>\mu</math>L or transfusion-dependent at baseline	Dose Adjustment or Response
<20,000/ $\mu$ L above base line or platelet transfusion requirement has not decreased following at least 2 weeks of eltrombopag	Increase daily dose by 25 mg (25 mg for East Asians) every 2 weeks to 150 mg/day for non East Asians (75mg/day for East Asians).
$\geq$ 20,000/ $\mu$ L above baseline but $\leq$ 200,000/ $\mu$ L following at least 2 weeks of eltrombopag	Keep at current dosage.
>200,000/ $\mu$ L (untransfused) at any time on study	Decrease dosage by 25 mg (25 mg for East Asians) every 2 weeks to lowest dosage that maintains platelet count $\geq$ 20,000/ $\mu$ L above baseline.
>400,000/ $\mu$ L (untransfused) at any time on study	Discontinue eltrombopag for one week, if platelets < 20,000; restart at 50% of current dose.

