**Dose Adjustments for Patients Entering with Anemia (Hb < 9.0gr/dL or transfusion-dependence)**

Depending on response and/or tolerability, the daily dose may be increased or decreased according to the following rules.

Hemoglobin < 9.0 gr/dL or transfusion dependent at baseline	Dose Adjustment or Response
hemoglobin rise of < 1.5 g/dL.	Increase daily dose by 25 mg (25 mg for East Asians) every 2 weeks to maximum 150mg/day for non- East Asians (75mg/day for East Asians).
$\geq$ 1.5g/dL above baseline but $\leq$ 13g/dL following at least 2 weeks of-eltrombopag	Keep at current dosage.
>13g/dL (untransfused) at any time on study	Decrease dosage by 50% to lowest dosage that maintains Hb $\geq$ 1.5g/dL above baseline.
>15g/uL (untransfused) at any time on study	Discontinue eltrombopag for one week, if Hb<13g/dL restart at 50% of current dose. Phlebotomy may be performed if clinically indicated as determined by the investigator.

If after dose escalation to 150 mg (or a maximum tolerated dose below 150 mg) there is no response within the study period, treatment will be discontinued and subjects will go off study per section 8.6. In the event that a subject is transfused platelets for a count >10,000/ $\mu$ L without a medical indication during the study period, the subject may continue on study drug and the response assessment may be extended for an additional 4 weeks at the discretion of the principal investigator.

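### Section 5.2 gives conflicting restart rules after a high-count hold: the platelet table restarts only below 20,000/µL, two restart doses are printed, and no rule is given precedence

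*Combined protocol and SAP*

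**What the plan says.** Section 5.2 ties the dosing rules to how the subject qualified: "dose adjustment criteria will vary depending on whether one or both lineages meet inclusion criteria".

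- **Platelet entrants (platelet table).** The dose rises while the count is less than 20,000/µL above baseline and is kept from there up to 200,000. Above 200,000 the instruction is "Decrease dosage by 25 mg (25 mg for East Asians) every 2 weeks to lowest dosage that maintains platelet count" at least 20,000 above baseline. Above 400,000 it is "Discontinue eltrombopag for one week, if platelets < 20,000; restart at 50% of current dose".
- **Anemia entrants (anemia table).** The hold row is ">15g/uL (untransfused) at any time on study" (unit read here as g/dL), with the action "Discontinue eltrombopag for one week, if Hb<13g/dL restart at 50% of current dose". On platelets in these subjects, the 5.2 text says "dose escalation for anemia will not be halted unless the platelet count goes above 400,000".
- **Dual entrants (5.2 text).** Escalation continues until both lineages reach the tables' keep-dose levels, unless platelets exceed 400,000 or "hemoglobin goes over 16.0 gr/dL, in which case drug will be discontinued for one week and the dose decreased by 50" percent.
- **Any entrant (closing sentence of the 5.2 text).** When a stopping platelet count or hemoglobin is reached, "eltrombopag will be discontinued for one week and restarted at the next lowest dose".

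Section 5.4.3 holds drug for one week at platelets above 400,000 or Hb above 16. It permits restart at half dose once counts are below those cutoffs. Section 5.5 carries the 5.2 dosing criteria into extended access.

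**The concern.** These are operative dosing and safety rules, and through 5.5 they continue to apply after week 20. After one and the same event, a platelet count above 400,000, the protocol prints three restart conditions (below 20,000; below 400,000; none) and two restart doses.

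The table's condition works against the dosing aim in the Precis, which is the lowest dose that keeps platelets at least 20,000 above baseline. The closing sentence errs the other way: read literally, it restarts drug after a week even if platelets are still above 400,000.

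The dose conflict bears most on subjects who entered on anemia alone. They have no platelet step-down before 400,000, and for a platelet-triggered hold only 5.4.3 tells staff to halve their dose. Whoever manages a hold has to choose a rule, so subjects in the same situation could be treated differently.

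**Working it through.** The plan states no figure here to reproduce. The check sets the rules side by side and then does simple arithmetic.

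**Rules after a hold**

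| Source | Applies to | Restart condition | Restart dose |
|---|---|---|---|
| 5.2 platelet table | platelet entrants | platelets <20,000 | 50% |
| 5.2 anemia table | anemia entrants | Hb <13 | 50% |
| 5.2 text, dual-entry sentence | dual entrants | one week, no count | 50% |
| 5.2 text, closing sentence | all entrants | one week, no count | one dose level lower (undefined) |
| 5.4.3 | no entry group named | platelets <400,000, Hb <16 | 50% |

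**1. Restart count.** The keep-dose level (platelet table) and the platelet count-response level (section 8.1) are both baseline B + 20,000. The printed restart is below 20,000, so it falls short of that level by more than (B + 20,000) − 20,000 = B. Count-based entry is at 30,000 or less (4.1.3).

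| B | Keep-dose/response level | Restart is below that level by more than | Relative to baseline |
|---|---|---|---|
| 10,000 | 30,000 | 10,000 | restart possible above baseline |
| 20,000 | 40,000 | 20,000 | only below baseline |
| 30,000 | 50,000 | 30,000 | only if more than 10,000 below baseline |

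Against 5.4.3 the difference is 400,000 − 20,000 = 380,000, a 20-fold ratio.

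The only off-drug kinetics in the documents are from ITP. In the repeat-dose study (2.4.6), median counts were above 100,000 one week after stopping and near baseline at two weeks. Section 2.9 gives a return to baseline within one to two weeks. So the condition could often be unmet at the one-week check and met later, except that a subject with a baseline of 20,000 to 30,000 who merely returns to baseline still does not meet it. MDS kinetics are not given.

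**2. Restart dose.** The next lower dose is not defined. Assume one 25-mg step, as in the escalation rule (2.6) and the liver rule (5.3.2). Gap = (dose − 25) − 0.5 × dose.

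| Dose (mg) | 50% | −25 mg | Gap |
|---|---|---|---|
| 150 | 75 | 125 | 50 |
| 125 | 62.5 | 100 | 37.5 |
| 100 | 50 | 75 | 25 |
| 75 (East Asian maximum) | 37.5 | 50 | 12.5 |
| 50 | 25 | 25 | 0 |

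From the East Asian starting dose of 25 mg, half is 12.5 mg and no 25-mg step remains. If the next lower dose were taken to mean halving, every gap would be zero.

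**3. Hemoglobin hold for dual entrants.** The anemia table, headed for patients entering with anemia, holds above 15. The dual-entry sentence and 5.4.3 hold above 16. An untransfused Hb above 15 and up to 16 is therefore held under one rule and not under the other, a difference of 1 g/dL.

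**The case against.** The strongest reply is that the protocol already contains a workable rule. Section 5.4.3 restarts drug at half dose once counts are below the cutoff, the preface to the platelet table is permissive, and 20,000 may be a slip for 200,000. Section 2.6 rates thrombocytosis in MDS as unlikely.

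Much of this stands, and it rules out several stronger readings that a reader might infer:

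- *Responders are kept off drug until severe thrombocytopenia returns.* That follows only if the table cell is read alone. Section 5.4.3 and the closing sentence of 5.2 both allow an earlier restart. The defect is a wrong or conflicting instruction, not a settled rule that withholds drug.
- *Hb 15 versus 16 is an error.* The 5.2 text says criteria vary with the number of qualifying lineages. A specific limit of 16 for dual entrants, leaving room to escalate for platelets, is coherent. But the same text sends dual entrants to the tables, so which limit governs needs saying.
- *The dose gap could be 62.5 mg, using the 12.5-mg tablet as the step.* No dosing rule uses a 12.5-mg step.
- *The label's thrombosis data show harm from the restart dose.* Five of six patients in that excerpt had events at platelets above 200,000 within 30 days of completing treatment, but they had chronic liver disease. This does not bear on restart dose in MDS.

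What the reply does not remove is that no sentence gives 5.4.3 precedence over 5.2, that 5.5 points to 5.2, and that a probable slip in a stop-and-restart rule still has to be corrected. That 200,000 was intended is an inference.

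**Conclusion.** Two parts are wrong as written. The platelet table's restart count is below its own keep-dose level for any baseline above zero, leaves 20,000 and above without a rule, and conflicts with 5.4.3 and with the closing sentence of 5.2. The closing sentence conflicts with every other statement of the restart dose, by 50 mg at 150 mg and by nothing at 50 mg if a step is 25 mg. The Hb hold level for dual entrants is an open question of precedence.

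The count comparison rests on printed values; the dose gap rests on the 25-mg assumption. The number of subjects affected is not stated and should be small. Sample size, alpha and power do not depend on these rules, and nothing in the documents shows that the primary result would change. The point should be corrected, but it does not undermine the design.

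**What to change.** - **(a) Platelet table, row above 400,000.** Replace the restart value with one the clinical team confirms: below 200,000 (the table's own step-down level) or below 400,000 (as in 5.4.3). Add that if the count is not yet below it after one week, drug stays held and the blood count is repeated weekly until it is. Changing the number alone would leave the same gap at a higher level.
- **(b) Closing sentence of the 5.2 text.** Change the ending to: *restarted at 50% of the current dose once the applicable restart count is met*. Halving the scheduled doses of 25 to 150 mg gives 12.5 to 75 mg, which can be made from the 12.5, 25, 50 and 75 mg tablets listed in section 11.1.
- **(c) Precedence.** State whether Hb 15 or 16 governs dual entrants, and that 5.4.3 applies to lineages that did not qualify the subject. The latter matters because an anemia entrant with, say, 250,000 platelets at baseline (an assumed example) could return to baseline and never meet a restart level of 200,000.

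The cost is a wording amendment to 5.2 and a scope sentence in 5.4.3, with no added patients or tablet strengths. Counts are already weekly through week 16 (6.2). In extended access 6.3 schedules them every one to three months, so a subject held there would need some extra counts. A restart level of 200,000 can lengthen some holds compared with 5.4.3, and choosing Hb 15 for dual entrants would add holds between 15 and 16 g/dL.

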**Dose Adjustments for Patients Entering with Anemia (Hb < 9.0gr/dL or transfusion-dependence)**

Depending on response and/or tolerability, the daily dose may be increased or decreased according to the following rules.

Hemoglobin < 9.0 gr/dL or transfusion dependent at baseline	Dose Adjustment or Response
hemoglobin rise of < 1.5 g/dL.	Increase daily dose by 25 mg (25 mg for East Asians) every 2 weeks to maximum 150mg/day for non- East Asians (75mg/day for East Asians).
$\geq$ 1.5g/dL above baseline but $\leq$ 13g/dL following at least 2 weeks of-eltrombopag	Keep at current dosage.
>13g/dL (untransfused) at any time on study	Decrease dosage by 50% to lowest dosage that maintains Hb $\geq$ 1.5g/dL above baseline.
>15g/uL (untransfused) at any time on study	Discontinue eltrombopag for one week, if Hb<13g/dL restart at 50% of current dose. Phlebotomy may be performed if clinically indicated as determined by the investigator.

If after dose escalation to 150 mg (or a maximum tolerated dose below 150 mg) there is no response within the study period, treatment will be discontinued and subjects will go off study per section 8.6. In the event that a subject is transfused platelets for a count >10,000/ $\mu$ L without a medical indication during the study period, the subject may continue on study drug and the response assessment may be extended for an additional 4 weeks at the discretion of the principal investigator.

### 5.3 Dose delays, modifications or discontinuation for non-hematologic side effects

**5.3.1 Infection:** Subjects who experience an infection requiring intravenous antibiotics will not have eltrombopag discontinued. If the subject experiences infection severe enough to require vasopressors or intubation, the drug will be withheld until the subject is stable.

**5.3.2 Liver function abnormalities:** In the event of an increase in the ALT level to > 6 times the ULN, -subjects will return to clinic or have blood tests drawn by their home physician every 3-4 days. If the ALT remains > 6 times the ULN on a second blood test, eltrombopag will be discontinued until ALT is < 5 times the ULN. Eltrombopag will be restarted at a dose level 25mg/day lower than the prior dose. If the toxicity appeared on a dose of 25 mg/day, eltrombopag will be discontinued permanently. If liver tests abnormalities return to and ALT of > 6 times ULN on this reduced dose, eltrombopag will be permanently discontinued.

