### 4. ELIGIBILITY ASSESSMENT

#### 4.1 Inclusion criteria

- 4.1.1 Diagnosis of MDS, with WHO classification of refractory anemia, refractory cytopenia with unilineage dysplasia (RCUD), RARS, RCMD-RS, or RCMD
- 4.1.2 IPSS risk scores of low, intermediate-1, or intermediate-2.
- 4.1.3 Platelet count  $\leq 30,000/\mu\text{L}$  or platelet-transfusion-dependence (requiring at least 4 platelet transfusions in the 8 weeks prior to study entry); OR hemoglobin less than 9.0 gr/dL or red cell

- transfusion-dependence (requiring at least 4 units of PRBCs in the eight weeks prior to study entry) OR ANC $\leq$ 500
- 4.1.4 Age  $\geq$  18 years old
  - 4.1.5 Treatment naïve or off all other treatments for MDS (except stable dosing of filgrastim (G-CSF), erythropoietin, and transfusion support) for at least four weeks. G-CSF can be used before, during and after the protocol treatment for subjects with documented neutropenia (<500/UL) as long as they meet the criteria for other cytopenias as stated above. G-CSF must be held for 3 weeks prior to enrollment bone marrow biopsy and prior to each study assessment bone marrow biopsy, unless clinically indicated to avoid infections per PI discretion.
  - 4.1.6 Adequate liver function, as evidenced by total serum bilirubin  $\leq$  1.5 times the upper limit of normal (patients with Gilbert's disease are eligible, provided intermittent indirect hyperbilirubinemia, AST or ALT  $\leq$  5 times the upper limit of normal).
  - 4.1.7 A serum creatinine concentration  $\leq$  2 x ULN

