## 8.6 Off Study Criteria

8.6.1 Per Subject choice: Subjects may withdraw from study at their request. The risks of withdrawing will be discussed, as will alternative treatment options. Those subjects who choose to withdraw while taking eltrombopag will be strongly encouraged to continue to have labs monitored until he/she initiates alternative therapy.

8.6.2 Per principal investigator decision: Should any of the following adverse events occur during the 16 to 20 week study period, or in the extension treatment arm in responders, eltrombopag will be discontinued. The subject will be followed until resolution of the event. Labs will be monitored through 30 days off study drug time point or until he/she initiates alternative disease directed therapy at which time the subject's participation on this study will be considered complete and the subject will go off study.

- Intolerance of eltrombopag not resolved by dose reduction
- Life threatening acute hypersensitivity reaction
- Thrombosis/embolism (DVT, PE, stroke or TIA, myocardial infarction) other than central line thrombosis
- Persistent hepatotoxicity as defined in section 5.3.2
- New or worsening morphological abnormalities or cytopenia(s) (see section 5.4.2)
- No treatment response by week 16, (20 weeks at P.I. discretion)
- Any Grade IV toxicity considered related to the study medication excluding readily reversible metabolic or laboratory abnormalities or hematologic toxicities
- Significant progression of disease or a concomitant condition that would make the subject ineligible for further protocol participation

- Pregnancy or unwillingness to use acceptable forms of contraception
- Initiation of non-protocol therapy for MDS
- Non-compliance with protocol
- Lost to follow-up
- Study completion

Once off study (either by per subject choice or per PI decision), subjects will be referred back to his or her referring physician or consented to the NHLBI evaluation and treatment protocol (94-H-0010) for consideration for standard therapy or evaluation for eligibility for another Branch protocol, depending on what is considered to be in the best interest of the subject.

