##### *Hepatotoxicity*

PROMACTA may increase the risk of severe and potentially life-threatening hepatotoxicity. Measure serum ALT, AST, and bilirubin prior to initiation of PROMACTA, every 2 weeks during the dose adjustment phase, and monthly following establishment of a stable dose. PROMACTA inhibits UDP-glucuronosyltransferase (UGT)1A1 and organic anion-transporting polypeptide (OATP)1B1, which may lead to indirect hyperbilirubinemia. If bilirubin is elevated, perform fractionation. Evaluate abnormal serum liver tests with repeat testing within 3 to 5 days. If the abnormalities are confirmed, monitor serum liver tests weekly until resolved or stabilized. Discontinue PROMACTA if ALT levels increase to greater than or equal to 3 x ULN in patients with normal liver function or greater than or equal to 3 x baseline (or greater than 5 x ULN, whichever is the lower) in patients with pre-treatment elevations in transaminases and are:

- progressively increasing, or
- persistent for greater than or equal to 4 weeks, or
- accompanied by increased direct bilirubin, or
- accompanied by clinical symptoms of liver injury or evidence for hepatic decompensation.

If the potential benefit for reinitiating treatment with PROMACTA is considered to outweigh the risk for hepatotoxicity, then consider cautiously reintroducing PROMACTA and measure serum liver tests weekly during the dose adjustment phase. Hepatotoxicity may reoccur if PROMACTA is reinitiated. If liver test abnormalities persist, worsen, or recur, then permanently discontinue PROMACTA.

Isolated cases of severe liver injury were identified in clinical trials. The elevation of liver laboratory values occurred approximately three months after initiation of PROMACTA. In all cases, the event resolved following PROMACTA discontinuation.

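### Liver rule 5.3.2 stops and restarts eltrombopag on ALT alone, so ALT of 3 to 6 x ULN with raised direct bilirubin or liver symptoms triggers no mandatory stop

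*Combined protocol and SAP*

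**What the plan says.** Every step of Section 5.3.2 is keyed to ALT. A value above 6 x ULN brings repeat testing every 3 to 4 days. Then: "If the ALT remains > 6 times the ULN on a second blood test, eltrombopag will be discontinued", until ALT is under 5 x ULN. After that, "Eltrombopag will be restarted at a dose level 25mg/day lower than the prior dose". The drug is stopped for good if ALT again exceeds 6 x ULN on the lower dose, or if the toxicity arose at 25 mg/day. Bilirubin, symptoms and decompensation are not mentioned. Section 8.6.2 lists "Persistent hepatotoxicity as defined in section 5.3.2" among its reasons to discontinue, and so adds no liver criterion of its own.

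Section 6.2 requires weekly chemistry to week 16. For draws by the home physician, 6.2 and 6.3 list transaminases and total bilirubin, not direct bilirubin. The components of the NIH hepatic panel are not given.

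The label excerpt in 10.3.1.2 (Hepatotoxicity) goes further. With normal liver function it stops the drug at ALT of 3 x ULN or more if one of four qualifiers applies. One is that the rise is "accompanied by increased direct bilirubin"; another is clinical evidence of liver injury or decompensation. With raised pre-treatment transaminases the threshold is 3 x baseline, "or greater than 5 x ULN, whichever is the lower". It also says: "If bilirubin is elevated, perform fractionation".

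On entry, 4.1.6 allows total bilirubin up to 1.5 x ULN and ALT or AST up to 5 x ULN. Patients with Gilbert's "disease are eligible, provided intermittent indirect hyperbilirubinemia".

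**The concern.** Hepatotoxicity is a boxed warning for this drug (10.3.1.1). A raised ALT with a raised direct bilirubin, or with symptoms, is more worrying than the same ALT alone, and 5.3.2 does not tell the two apart. Total bilirubin cannot do so reliably here: 10.3.1.2 notes that the drug can itself cause indirect hyperbilirubinemia, and Gilbert's patients may enroll. Without the direct fraction, a benign rise and a sign of liver injury can look the same on a home report.

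Restart has the same weakness. After a 6 x ULN stop, 5.3.2 directs resumption once ALT is under 5 x ULN, even if direct bilirubin is still raised or symptoms persist.

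The severe cases described in 10.3.1.2 all resolved on discontinuation, and "The elevation of liver laboratory values occurred approximately three months after initiation of PROMACTA". At that time subjects here are still having weekly panels, so testing is frequent enough. What is missing is the criterion and, on home draws, the measurement it would need.

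**Working it through.** This is mainly a comparison of texts; no design figure needs reproducing.

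**1. Uncovered range of ALT.** Let b be baseline ALT in multiples of ULN. For a subject who also has raised direct bilirubin or symptoms, the label excerpt stops at 3 x ULN if baseline is normal, and at the lower of 3b and 5 if baseline is raised. Section 5.3.2 stops only at confirmed ALT above 6.

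| Baseline ALT (x ULN) | Label threshold (x ULN) | 5.3.2 threshold (x ULN) | No mandatory stop (x ULN) |
|---|---|---|---|
| Normal | 3 | 6 | 3 to 6 |
| 1.2 | 3 x 1.2 = 3.6 | 6 | 3.6 to 6 |
| 1.5 | 3 x 1.5 = 4.5 | 6 | 4.5 to 6 |
| 5/3 = 1.67 or more | 5 | 6 | 5 to 6 |

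Example: normal baseline, ALT 4 x ULN, direct bilirubin raised. The excerpt says stop. Section 5.3.2 requires neither a stop nor a repeat test.

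**2. Restart.** With normal baseline, ALT of 3 to just under 5 x ULN and direct bilirubin still raised, 5.3.2 resumes the drug while the excerpt's stop condition is still met.

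**3. Is the direct fraction available?** There are 16 weekly panels to week 16, and only the week 16 visit must take place at NIH (6.2). Up to 16 - 1 = 15 of the 16 may therefore be home draws carrying total bilirubin only. This is a permitted extreme, not an expected pattern.

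**4. Dose when the severe cases arose.** From 50 mg, steps of 25 mg every 2 weeks reach 150 mg after (150 - 50)/25 = 4 steps, or 8 weeks. For East Asian subjects, 25 mg reaches the 75 mg cap after (75 - 25)/25 = 2 steps, or 4 weeks. A subject without a response can thus be at the top dose by three months. For non-East Asian subjects that dose is 150/75 = 2 times the highest dose in the ITP dose-response data in 2.6. Section 5.2 continues escalation unless a toxicity-related laboratory limit is met, and the only hepatic limit defined is the ALT value in 5.3.2.

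**5. Frequency.** The documents give no rate for ALT of 3 to 6 x ULN with raised direct bilirubin or symptoms in this population, so no expected number of subjects is offered.

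**The case against.** The strongest reply is that investigators are not powerless. Section 2.6 limits escalation to subjects who tolerated the last dose, and 5.5 conditions extended treatment on there being no contraindication. Section 8.6.2 lists intolerance, related Grade IV toxicity, and a concomitant condition that would end eligibility. That last item can be read with the bilirubin limit in 4.1.6 and the bar on severe concurrent hepatic disease in 4.2.7. Section 9.2.2 has symptomatic laboratory changes collected and the action on study drug recorded when a result is clinically significant. The label text is in the protocol, and nothing forbids fractionation on a home draw.

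This stands as far as it goes. A reader might infer that the protocol forces treatment to continue in a jaundiced subject; these routes show that it does not. But they are discretionary, or they concern recording. None requires a stop at a stated hepatic finding. The Grade IV item applies late and leaves out readily reversible laboratory abnormalities.

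A reader might also infer that 5.3.2 contradicts a binding label rule. Section 10.3.1 presents the label text as excerpted risk information, so it is a reference point and not a second trial rule. It is fair to ask why two of its four qualifiers should be taken up. The other two, a progressive rise and persistence for 4 weeks, concern ALT on its own, where a higher threshold is a legitimate design choice.

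The dose argument is context only. The remark in 2.4.6 on high plasma concentrations in 2 subjects with ALT and AST above 3 x ULN sits in an item on Asian subjects, whose dose this protocol already lowers and caps. Section 2.6 reports good tolerance up to 200 mg for 5 days in healthy subjects and no apparent safety issue at 100 mg in cancer patients dosed for 10 days, though these were short exposures.

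**Conclusion.** The gap is real and cheap to close. Below confirmed ALT of 6 x ULN, no defined criterion stops the drug for raised direct bilirubin or symptoms of liver injury, and restart ignores both. The uncovered range is 3 to 6 x ULN with normal baseline ALT, narrowing to 5 to 6 x ULN from a baseline of about 1.67 x ULN.

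This rests on three readings: 5.3.2 is the operative rule, the home lists state what must be measured, and the transaminase limit in 4.1.6 applies to all entrants.

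The consequence is for patient safety only. Sample size, error rates and the analysis method are unaffected. With no event rate in the documents, the point should not be presented as a likely event.

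Two further inferences are not supported. One is that 6 x ULN is wrong for isolated ALT; nothing here shows that. The other is that panels in extended access are too sparse. Section 6.3 lets the investigator evaluate more often when medically indicated, and the documents give no basis for a particular tighter schedule.

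**What to change.** In 5.3.2, and so by reference in 8.6.2, add a hold with no dose escalation when both parts are met:

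- ALT is at least 3 x ULN or, with raised baseline, at the lower of at least 3 x baseline and above 5 x ULN; and
- direct bilirubin is above both the laboratory ULN and the subject's own baseline, or there are symptoms of liver injury or hepatic decompensation.

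The double condition on direct bilirubin matters for subjects who enter with ALT near 5 x ULN, in whom a small ALT rise would meet the first part.

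In 6.2 and 6.3, require fractionation of any raised total bilirubin, home draws included. The MDS/AML expected-event list in 10.3.1.2 warns that serum discoloration can interfere with some colorimetric methods. It does not say whether bilirubin assays are affected, so ask for an unaffected method where discoloration is suspected.

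Allow restart after this hold, or after the 6 x ULN stop, only when direct bilirubin and symptoms are back to baseline and ALT is below the relevant threshold (the hold trigger, or the existing 5 x ULN). The isolated-ALT threshold may stay.

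The cost is a few sentences and a reflex test on blood already drawn, with no extra visit. If every weekly panel in 30 subjects needed it, that would be 30 x 16 = 480 results over 16 weeks, or 30 x 20 = 600 over 20; in practice it is needed only where total bilirubin is raised. A few more interruptions will follow. Under 8.3, a subject who withdraws for toxicity before the week 16 or 20 assessment counts as a non-responder, so each one costs 1/25 = 4 percentage points of response rate.
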